8.1.5.4 Coding of specimens for privacy protection

Specimens will be coded for privacy protection.

9. STUDY CALENDAR

	BS	Post-Transplant Day							
		±5 days	±5 days	±10 days	± 2 wks	± 2 wks	± 2 wks	± 4 wks	± 4 wks
		d+30	d+60	d+90	d+180	d+270	d+365	d+540	d+730
Informed Consent	X								
Path Review	X								
H&P/KPS	X								
PFT	X								
Echo	X								
CBC with diff	X								
Chemistry: BMT I	X								
HLA confirmed	X								
BMT Panel (serologies)	X								
CXR	X								
EKG	X								
STR subsets: PB		X	X	X	X	X	X**		X
BM bx/asp**	X			X			X		X
Research Samples		X	X	X	X				
Skin Biopsy	X			X					
Flowcytometry** (SS only)		X		X	X	X	X	X	X
Disease Status/Response**	X			X		X	X	X	X
GVHD assessment	X	X	X	X	X	X	X		X

** Per Attending Physician's discretion

Correlative Study Calendar

	Donor Chimerism	Chemokine Receptor Profile	Th1/Th2 Phenotype	Treg Cell Quantity	Treg Cell Function	Skin Biopsy Pathology	Skin Biopsy T Cell Trafficking	Derm Clinical Assessment	Bone Marrow Biopsy	CTL Assay	Tumor Cell Banking
Pre TSEBT		X		X		X		X	X	X	Sezary only
Pre TLI/ATG		X		X		X	First 5 pt	X			
Pre Infusion		X		X							
+ 30 day	X	X	X	X	First 5 pt			X			
+ 60 day	X	X	X	X				X			
+ 90 day	X	X	X	X	First 5 pt	X	First 5 pt	X	X	X	
+ 180 day	X	X	X	X	First 5 pt		First 5 pt	X	X	X	
+ 270 day	X	X	X	X				X			
+ 1 year	X	X	X	X	First 5 pt		First 5 pt	X	X	X	
+ 2 year	X							X	X		
Cell Product		X	X	X							
Pre ECP		X	X	X							
Post ECP		X	X	X							
Disease Regression						X		X			
Disease Progression						X		X			
Sample		Up to 5 GGT			5 mm punch	5 mm punch		Routine	2 GTT for effector	2 GTT	
Site	HLA Lab	HIMC	CTF	CTF	CTF	Path	CTF	Cut Lym Clinic		HIMC	HIMC
Assay	Chimerism: CD3, CD19, CD56, CD15	Skin: CCR4, CCR10, CLA; LN: CCR7	Th1: IL-2, IFN γ ; Th2: IL-4, IL-10	FoxP3 positive	Inhibition of MLR	Monitoring Residual Disease	Lymphocyte Donor Chimerism, Chemokine receptor		FAM-VAD Assay	Use as Target Cell for CTL	

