4.1.6 Engraftment and Disease Status Monitoring

- s) Patients will be followed in the ITA for signs of infection or GVHD. Monitoring for engraftment and infection will be according to current standard of care of Stanford BMT program.
- t) Chimerism: Microsatellite analysis (VNTR) of CD3, CD19, CD15, and CD56 peripheral blood cell subsets will be performed on days +28 (\pm 5 days), +56 (\pm 5 days), +90 (\pm 14 days), +180 (\pm 14 days), +270 (\pm 14 days), and yearly (\pm 4 weeks) to evaluate the degree of donor hematopoietic cell engraftment (donor chimerism), and on bone marrow on day +90 (\pm 14 days), and yearly per physician's discretion.
- u) Clinical response will be determined at 3, 6, 9, 12, 18, 24 months or until relapse or progression after transplant. The disease status and clinical response will be scored on a rigorous and multifactorial approach described before (41, appendix). This approach takes tumor burden in skin, lymph nodes and blood into consideration. To achieve this, patients will be evaluated at Cutaneous Lymphoma Clinic before transplant and at specified time points after transplant.

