10. MEASUREMENT OF EFFECT

The measurement of effect is determined by clinical response to non-myeloablative allogeneic HSCT. The clinical response will be assessed by a rigorous and multifactorial approach described before (41, appendix). This approach takes tumor burden in skin, lymph nodes and blood into consideration. To achieve this, patients will be evaluated at Cutaneous Lymphoma Clinic before transplant and at specified time points after transplant.

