10.1 Anti-tumor Effect

10.1.1 Definitions

Disease status will be evaluated right before non-myeloablative allogeneic transplants and at 3, 6, 9, 12, 18, 24 months after allogeneic transplant or up to 1st recurrence or progression.

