12.1 Endpoints

12.1.1 Primary endpoint

The primary efficacy endpoint is PFS at 180 days (defined above). The safety endpoints include GVHD and other treatment related events, including mortality.

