12.3.2 Evaluation of Efficacy

Efficacy will be evaluated by calculating the Kaplan-Meier estimates of progression-free survival (PFS, i.e., probability of remaining alive and free of progression). We will also calculate the cumulative incidence estimate of the progression rate, using non-relapse mortality as a competing risk.

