12.3.3 Methods for handling missing data and non-adherence to protocol

We do not expect to have missing data on key outcome variables, and non-adherence to protocol presumably is limited to failure to complete the entire process of preparation and transplant; this will be handled by subgroup analyses as described.

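### The study calendar omits the day +180 disease assessment and makes the whole row discretionary, contradicting sections 4.1.6(u) and 10.1.1 at the visit that decides the primary endpoint, PFS at 180 days

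*Combined protocol and SAP*

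**What the plan says.** - **Section 4.1.6(u):** "Clinical response will be determined at 3, 6, 9, 12, 18, 24 months or until relapse or progression after transplant".
- **Section 10.1.1:** disease status is evaluated just before transplant and "at 3, 6, 9, 12, 18, 24 months after allogeneic transplant or up to 1st recurrence or progression". Neither section leaves this to anyone's judgement.
- **Section 10:** "patients will be evaluated at Cutaneous Lymphoma Clinic before transplant and at specified time points after transplant".
- **Section 9, main calendar:** the row "Disease Status/Response" has an X at baseline, d+90, d+270, d+365, d+540 and d+730, and none at d+180. It carries a double asterisk, explained as "Per Attending Physician's discretion". The visit window at d+180 is ±2 weeks.
- **Section 9, correlative calendar:** a dermatology clinical assessment in the Cutaneous Lymphoma Clinic is marked at +180 days, without an asterisk.
- **Section 12.1.1:** "The primary efficacy endpoint is PFS at 180 days (defined above"). **Section 12.3.2:** "Efficacy will be evaluated by calculating the Kaplan-Meier estimates of progression-free survival".
- **Section 10.1.6**, under the PFS heading, defines EFS and dates recurrence by its first documentation.
- **Section 12.3.3:** "We do not expect to have missing data on key outcome variables". It gives no rule for a 6-month assessment that was not done.

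**The concern.** Of the six post-transplant assessments that the text requires, the only one missing from the calendar row is the one on which the primary endpoint turns. The discretion mark also makes the other five optional, including d+90. Nothing says which section governs.

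A Kaplan-Meier estimate uses the date on which progression is recorded. A patient who progresses between days 90 and 180, and whose progression is next looked for at d+270, is event-free at day 180 in the analysis. The error goes in one direction, and the confidence interval does not allow for it. Section 12.4.2 contrasts a 75% target with results nearer 50%, which it would not find encouraging, so an upward shift bears directly on how the result is read.

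The ±2-week window raises a related question. Section 12 does not say whether progression first found on days 181-194 counts toward the 180-day endpoint.

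**Working it through.** **1. The calendar row.** Cell by cell, the disease-status row reads: baseline X, d+30 blank, d+60 blank, d+90 X, d+180 blank, d+270 X, d+365 X, d+540 X, d+730 X. The flow-cytometry row above it and the GVHD row below it both show an X at d+180, so a column shift in the text extraction is unlikely. The cell should still be checked against the PDF.

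**2. The plan's own precision figure.** The exact (Clopper-Pearson) 95% interval for 27/36 is 57.8% to 87.9%, half-width 15.0%. This matches the 58% to 88% and 15% in section 12.4.2. Neither the sample size nor this interval changes with the fix.

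**3. Bias from the missing visit.** Inputs:
- S, true 180-day PFS: 0.75 (target) and 0.50 (not encouraging), both from section 12.4.2, and 0.60 as an intermediate value.
- NRM, non-relapse death by day 180: 5% (180-day transplant-related mortality in the earlier TLI/ATG series, section 2.2), 10% (assumed), and 15% (one-year allogeneic mortality in the meta-analysis of section 2.1, used as a high value).
- u, the share of day 90-180 progressions not detected by day 180. The documents give no value, so the whole range is shown.
- Assumed: constant hazard, and patients with undetected progression do not die before day 180.

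Under a constant hazard, PFS at day 90 is √S, so a fraction √S − S of patients has its event in days 90-180: 0.116, 0.175 and 0.207 for S = 0.75, 0.60 and 0.50. The share of events that are progressions is q = 1 − NRM/(1 − S). Then

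observed PFS180 = S + q·u·(√S − S).

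Example: S = 0.75, NRM 5%, u = 1 gives q = 1 − 0.05/0.25 = 0.80, and 0.75 + 0.80 × 0.116 = 0.843.

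| True S | u = 0 | u = 25% | u = 50% | u = 100% | all events progressions, none detected |
|---|---|---|---|---|---|
| 0.75 | 0.750 | 0.762-0.773 | 0.773-0.796 | 0.796-0.843 | 0.866 |
| 0.60 | 0.600 | 0.627-0.638 | 0.655-0.676 | 0.709-0.753 | 0.775 |
| 0.50 | 0.500 | 0.536-0.547 | 0.572-0.593 | 0.645-0.686 | 0.707 |

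Ranges run from NRM 15% to NRM 5%. In a 36-patient study with S = 0.75 and u = 1, the number misdated is 36 × q × 0.116 = 3.3, 2.5 or 1.7 for NRM 5, 10 or 15%.

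**4. Sensitivity to the hazard shape.** If three quarters of day-180 progressions occur by d+90, observed PFS180 = S + 0.25·u·(1 − S − NRM). For u = 25% to 100% this gives 0.756-0.800 at S = 0.75 and 0.522-0.613 at S = 0.50.

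**5. The window.** A simulation of 2,000,000 patients per scenario used uniform visit windows (d+90 ±10 days, d+180 ±14 days) and no detection between visits. Entries are for NRM 5/10/15%.

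| Schedule and rule | True 0.75 | True 0.50 |
|---|---|---|
| Calendar only, read at day 180 | 0.843/0.820/0.796 | 0.686/0.666/0.645 |
| d+180 visit restored, read at day 180 | 0.800/0.788/0.775 | 0.600/0.589/0.578 |
| d+180 visit restored, read at day 194 | 0.747/0.744/0.740 | 0.497/0.495/0.493 |
| Progression status at the 6-month visit plus deaths to day 180 | 0.750 | 0.500 |

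The blank cell alone therefore adds about 2-4 points at true 75% (0.843 − 0.800 down to 0.796 − 0.775) and 7-9 points at true 50%. The rest comes from about half of the 6-month visits falling after day 180.

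**The case against.** The strongest reply is that the blank is probably clerical and that detection would not depend on it. Two text sections require the 6-month assessment. The Sezary flow-cytometry schedule in section 4.1.7(w) follows the same months and has its d+180 mark. The main calendar is plainly not exhaustive, since history and physical, blood count and chemistry appear only at baseline. The +180 dermatology assessment takes place in the clinic that sections 4.1.6(u) and 10 name for response evaluation, and skin progression seen there would count, because Appendix C makes progression in any compartment global progression. The correlative calendar also has event-triggered progression and regression rows, and section 4.1.7(v) foresees acting on progression before day +120. A value of u near 100% requires all of this to fail. The design is precision-based with no formal threshold, and a 1-2 point shift at u = 25% is small against a 15-point half-width.

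Much of this stands as to size. A large u is unlikely, the upper figures are limits rather than forecasts, and half or more of the calendar-only excess would remain if the visit were restored without a window rule.

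It does not remove the contradiction. No section says that the dermatology visit is the four-compartment Appendix C score. That column is also marked at +30 and +60 days, where no response assessment is scheduled, and has no 18-month entry, where one is. Flow cytometry at d+180 is for Sezary patients only and is itself discretionary.

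**Conclusion.** The concern holds. The documents disagree on whether the 6-month disease assessment exists and on whether it is mandatory, at the visit that determines the primary endpoint. That much is certain from the text, subject to a check of the cell in the PDF.

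The direction of any resulting bias is also clear: it can only raise 180-day PFS. Its size is not known. It is zero from the missing visit if sections 4.1.6(u) and 10.1.1 are carried out and used. Under the constant-hazard assumptions a true 75% reads 76-77%, 77-80% or 80-84% as the undetected share goes from 25% to 50% to 100%, with 87% as the outer limit. The unstated window rule matters about as much: with the visit restored but the curve read at day 180, a true 75% still reads about 77-80%. Because this affects the primary endpoint and costs little to repair, it must be fixed.

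**What to change.** 1. Reconcile section 9 with sections 4.1.6(u) and 10.1.1: mark the disease-status row at d+180 and remove the discretion mark from that row for patients without prior progression, relapse or death.
2. State whether the +180 dermatology assessment is the full Appendix C global score or only its skin component.
3. State in sections 12.1.1 and 12.3.2 that progression first found at the 6-month visit, within its ±2-week window, counts as an event for the 180-day endpoint. Either progression status at that visit plus deaths to day 180, or reading the curve at the end of the window, would serve. Choose one in advance.

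The cost is one calendar cell, one footnote mark and a few sentences. Patients already attend at d+180 for chimerism, GVHD assessment, research samples and the dermatology visit. Compared with following the calendar alone, it adds one disease evaluation per patient still at risk, possibly including nodal or visceral assessment where those sites are involved (section 9 has no cross-sectional imaging row). Reported PFS may be slightly less favourable.

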10. MEASUREMENT OF EFFECT

The measurement of effect is determined by clinical response to non-myeloablative allogeneic HSCT. The clinical response will be assessed by a rigorous and multifactorial approach described before (41, appendix). This approach takes tumor burden in skin, lymph nodes and blood into consideration. To achieve this, patients will be evaluated at Cutaneous Lymphoma Clinic before transplant and at specified time points after transplant.

10.1 Anti-tumor Effect

10.1.1 Definitions

Disease status will be evaluated right before non-myeloablative allogeneic transplants and at 3, 6, 9, 12, 18, 24 months after allogeneic transplant or up to 1st recurrence or progression.

10.1.2 Disease Parameters

Measurable diseases include skin, lymph node, viscera and blood Sezary cells.

10.1.3 Methods for Evaluation of Measurable Disease

Please refer to Appendix C.

10.1.4 Response Criteria

10.1.4.1 Evaluation of Target Lesions

Please refer to appendix.

10.1.4.2 Evaluation of Non-Target Lesions

N/A

10.1.4.3 Evaluation of Best Overall Response

Clinical response will be determined at different time points after allogeneic transplant.

10.1.5 Duration of Response

Duration of overall response is time measurement between first compete response and the first recurrent documentation.

10.1.6 Progression-Free Survival (or other parameters)

Event-free survival (EFS) is the time measurement between the day of allogeneic transplant and the first documented recurrence or death from any cause. Overall survival (OS) is the time measurement between the day of allogeneic transplant and death from any cause.

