2.3 Rationale

Mycosis Fungoides (MF) and its leukemic variant, Sezary Syndrome (SS) is the most common type of cutaneous non-Hodgkin's lymphoma (NHL) in North America. Though most of the patients have an indolent course with median survival of 12-15 years, those with advanced diseases have a survival of 1-3 years after diagnosis, and there is no curative therapy (1). While localized skin treatment, novel biological therapies such as histone deacetylase inhibitors, or systemic chemotherapy can temperately control the diseases, none of these provide a long-term remission. Graft-versus-lymphoma effects after allogeneic hematopoietic stem cell transplantation (HSCT) have been demonstrated to provide a long-term disease control in B cell lymphoma, including low-grade B cell lymphoma and chronic lymphocytic leukemia. We propose a clinical trial using non-myeloablative allogeneic HSCT to treat patients with advanced stage MF/SS. The rationale is that graft-versus-lymphoma provided by this non-myeloablative approach will result in a clinical response and a prolonged progression free survival in these patients. The patient population enrolled in this clinical trial will be those with MF/SS who still have persistent or progressive disease after being treated with multiple lines of local and systemic therapies. When MF/SS reached this stage of their disease, the conventional chemotherapies will no longer provide any clinical benefit. Therefore, we proposed using this low toxicity allogeneic HSCT protocol to these patients.

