Appendix C

Response criteria for Mycosis fungoides and Sezary Syndrome

Clinical Endpoints and Response Criteria in Mycosis Fungoides and Sezary Syndrome: a Joint Consensus Statement of the International Society for Cutaneous Lymphomas (ISCL), the United States Consortium for Cutaneous Lymphomas (USCCL) and the Cutaneous Lymphoma Task Force of the European Organization for Research and Treatment of Cancer (EORTC)

The global response criteria uses scoring system for the following four organ involvement systems: skin, lymph node, blood and viscera. Based on the response score of individual systems, a global response score will be given for individual patient. The skin disease burden will be measured using the modified severity weighted assessment tool (mSWAT); the skin responses are recorded and assessed as changes of the mSWAT score.

Response in Skin*

Complete response (CR)	100% clearance of skin lesions [#]
Partial response (PR)	50-99% clearance of skin disease from baseline without new tumors (T ₃) in patients with T ₁ , T ₂ or T ₄ only skin disease
Stable disease (SD)	<25% increase to <50% clearance in skin disease from baseline without new tumors (T ₃) in patients with T ₁ , T ₂ or T ₄ only skin disease
Progressive disease (PD)♦	(1) $\geq 25\%$ increase in skin disease from baseline or (2) New tumors (T ₃) in patients with T ₁ , T ₂ or T ₄ only skin disease or (3) Loss of response: in those with CR or PR, increase of skin score of greater than the sum of nadir plus 50% baseline score
Relapse	Any disease recurrence in those with CR

*Based on mSWAT score.

[#] A biopsy of normal appearing skin is unnecessary to assign a CR. However, a skin biopsy should be performed of a representative area of the skin if there is any question of residual disease where otherwise a CR would exist. If histologic features are suspicious or suggestive of MF/SS (see histologic criteria for early MF⁷), the response should be considered a PR only.

♦ Whichever criterion occurs first.

Response in Lymph Nodes*

CR	All lymph nodes are now <1.5 cm in greatest transverse (long axis) diameter by method used to assess lymph nodes at baseline or biopsy negative for lymphoma. In addition, lymph nodes that were N ₃ classification and <1.5 cm in long axis diameter at baseline, must now be ≤ 1 cm in diameter of the short axis or biopsy negative for lymphoma.

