PR	(1) Cumulative reduction $\geq 50\%$ of the SPD sum of the maximum linear dimension (major axis) x longest perpendicular dimension (minor axis) of each abnormal lymph node at baseline and no new lymph node ≥ 1.5 cm or >1.0 cm in the short axis if long axis 1-1.5cm diameter.
SD	Fails to attain the criteria for CR, PR and PD
PD ♦	(1) $>50\%$ increase in SPD from baseline of lymph nodes or (2) Any new node ≥ 1.5 cm in greatest transverse diameter or >1 cm in short axis diameter if 1-1.5 cm in long axis that is proven to be N ₃ histologically or (3) Loss of response: in those with PR or CR, $>50\%$ increase from nadir in SPD of lymph nodes
Relapse	Any new lymph node ≥ 1.5 cm in long axis diameter in those with CR

* Peripheral and central lymph nodes.

♦ Whichever criterion occurs first.

Response in Blood*

CR**	B_0
PR [#]	>50% decrease in quantitative measurements of blood tumor burden from baseline in those with high tumor burden at baseline (B_2)
SD	Fails to attain criteria for CR, PR or PD
PD [*]	(1) B_0 to B_2 or (2) >50% increase from baseline and at least 5,000 neoplastic cells/ μ L ⁴² or (3) Loss of response: 1. in those with CR who were B_1 or B_2 at baseline, increase in neoplastic >1000 neoplastic cells/ μ L or 2. in those with PR who were originally B_2 at baseline, >50% increase from nadir and at least 5,000 neoplastic cells/ μ L
Relapse	Increase of neoplastic blood lymphocytes to $\geq B_1$ in those with CR

* As determined by absolute numbers of neoplastic cells/uL.

** If a bone marrow biopsy was performed at baseline and determined to unequivocally be indicative of lymphomatous involvement, then to confirm a global CR where blood assessment now meets criteria for B_0 , a repeat bone marrow biopsy must show no residual disease or the response should be considered a PR only.

There is no PR in those with B_1 disease at baseline as the difference within the range of neoplastic cells that define B_1 is not considered significant and should not affect determination of global objective response.

* Whichever occurs first.

Response in Viscera

CR	Liver or spleen or any organ considered involved at baseline should not be enlarged on physical exam and should be considered normal by imaging. No nodules should be present on imaging of liver or spleen. Any post treatment mass must be determined to be biopsy to be negative for lymphoma.

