PR	>50% regression in any splenic or liver nodules, or in measurable disease (SPD) in any organs abnormal at baseline. No increase in size of liver or spleen and no new sites of involvement.
SD	Fails to attain the criteria for CR, PR or PD
PD [*]	(1) >50% increase in size (SPD) of any organs involved at baseline or (2) New organ involvement or (3) Loss of response: in those with PR or CR, >50% increase from nadir in the size (SPD) of any previous organ involvement
Relapse	New organ involvement in those with CR

*Use of FDG-PET scan in this instance is compatible with other NHLs but there is a paucity of data in clinical trials of MF/SS to document its utility.

*Whichever criterion occurs first.

Global Response Score

Global Score*	Definition	Skin	Nodes	Blood	Viscera
CR	Complete disappearance of all clinical evidence of disease	CR			All categories have CR/NI
PR	Regression of measurable disease	CR			All categories do not have a CR/NI and no category has a PD
		PR			No category has a PD and if any other category involved at baseline, at least one has a CR or PR
SD	Failure to attain CR, PR or PD representative of all disease	PR			No category has a PD and if any other category involved at baseline, no CR or PR in any
		SD			CR/NI, PR, SD in any category and no category has a PD
PD	Progressive disease				PD in any category
Relapse	Recurrence disease in prior CR				Relapse in any category

NI = non-involved

*It is recommended that not only the proportion of patients who achieve a response or an unfavorable outcome be calculated but a life table account for the length of the interval during which each patient is under observation.

Record of Changes

Date	Protocol Changes	IRB
------	------------------	-----

		Approval Date
March 11, 2009	Original protocol	April 21, 2009
April 29, 2009	Request of the SRC for clarifications in the statistical section	May 19, 2009
June 29, 2009	Changed eligibility criteria related to prior malignancies. Clarified collection goals and processing. Changed CSA taper to begin when chimerism studies obtained. Added timeframes for chimerism evaluations. Added tumor assessments to study calendar. Updated study calendar. Added research sample calendar. Changed fasting before ECP to a low fat diet.	July 14, 2009
March 30, 2010	Decreased TLI from 1200 cGy to 800 cGy. Length of treatment and dose of TSEBT will be determined by the radiation oncologist.	April 20, 2010

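### EFS in section 10.1.6 omits progression as an event, and the primary PFS endpoint refers back to that definition although 12.3.2 gives PFS a different event set

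*Combined protocol and SAP*

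**What the plan says.** Section 10.1.6, under the heading Progression-Free Survival, defines only EFS and OS. EFS ends at "the first documented recurrence or death from any cause".

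Section 12.1.1 states: "The primary efficacy endpoint is PFS at 180 days (defined above", with the bracket closing there. Section 12.3.2 describes PFS as the "probability of remaining alive and free of progression". It adds a cumulative incidence of progression, with non-relapse mortality as the competing risk.

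Appendix C keeps PD and Relapse as separate global categories. Global Relapse is "Recurrence disease in prior CR", and skin Relapse is "Any disease recurrence in those with CR". PD is not limited to patients who have responded, but it does include loss of response after CR. For skin the criterion reads "Loss of response: in those with CR or PR, increase of skin score of greater than the sum of nadir plus 50% baseline score".

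Section 1.1 names EFS in the primary objective and 12.1.2 lists it as a secondary endpoint. Section 2.3 describes the enrolled patients as those "who still have persistent or progressive disease after being treated with multiple lines of local and systemic therapies".

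**The concern.** A patient who goes to transplant with residual disease and never clears it cannot recur in the Appendix C sense. If that patient's disease then worsens, the EFS rule as written records nothing until death, although the treatment has failed. With a population described as having persistent or progressive disease, this route to failure has to be expected.

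The problem reaches the primary endpoint through the cross-reference. An analyst who follows 12.1.1 back to the PFS heading finds recurrence or death. An analyst who follows 12.3.2 uses progression or death. The two event sets can give different 180-day results from the same patients, and nothing in the plan says which governs. Section 10.1.7 plans no external response review, so the written definition carries much of the weight.

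**Working it through.** **Step 1: what recurrence means in section 10.1.6.** Four other places bear on it.
- Section 4.1.6 runs response assessment until relapse or progression, naming both.
- Section 10.1.1 evaluates disease up to first recurrence or progression, again naming both.
- Section 10.1.5 measures duration of response from first complete response to first documented recurrence, so recurrence there follows CR.
- Appendix C has no recurrence category other than Relapse, which requires prior CR.

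Section 10.1.6 keeps one of the two failures named in 10.1.1 and drops the other.

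**Step 2: map each failure to the two definitions, read literally.**

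| Failure after transplant | EFS, 10.1.6 | PFS, 12.3.2 |
|---|---|---|
| Death from any cause | event | event |
| PD in a patient never in CR | no event until death | event |
| Relapse from CR that also meets a PD criterion | event | event |
| Relapse from CR below every PD threshold | event | no event, or a later one |

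**Step 3: how wide the PFS gap is, by organ system (Appendix C).**
- Skin: any recurrence after CR is Relapse. Loss-of-response PD needs a score above nadir plus 50% of baseline. In CR the nadir is 0, so with an assumed baseline mSWAT of 60 the threshold is 0 + 0.5 × 60 = 30. A recurrence up to 30 is Relapse but not PD, unless new tumors appear in T1, T2 or T4 disease.
- Blood: a rise to B1 or above is Relapse. After CR, PD needs more than 1000 neoplastic cells/µL (B1 or B2 at baseline) or a move from B0 to B2.
- Nodes: a new node of at least 1.5 cm is Relapse. It is PD only if proven N3 histologically or if another nodal PD criterion is met.
- Viscera: new organ involvement is both Relapse and PD, so there is no gap.

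A relapse below threshold may later become PD. However, scheduled evaluation under 10.1.1 ends at first recurrence, so that later PD need not be documented.

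**Step 4: cumulative incidence.** The event is progression and the competing event is non-relapse mortality. A death after a sub-threshold relapse fits neither.

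**Step 5: scale.** The plan's own precision figure (12.4.2) is 27/36 with a 95% interval of 58% to 88% and a half-width of 15%. The exact (Clopper-Pearson) limits are the 0.025 quantile of Beta(27, 10) and the 0.975 quantile of Beta(28, 9). These are 57.8% and 87.9%, half-width 15.0%, so the figure reproduces.

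With complete follow-up to the time point, each failure left uncounted in a patient still alive raises the estimate by 1/n: 1/40 = 2.5 points, or 1/36 = 2.8 points. As an illustration, suppose 27 of 36 are counted event-free at day 180 and m of them had an uncounted failure. The number m is an assumption; the documents give none.

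| m | Estimate with all failures counted | Exact 95% CI |
|---|---|---|
| 0 | 27/36 = 75.0% | 57.8 to 87.9 |
| 1 | 26/36 = 72.2% | 54.8 to 85.8 |
| 3 | 24/36 = 66.7% | 49.0 to 81.4 |
| 5 | 22/36 = 61.1% | 43.5 to 76.9 |
| 9 | 18/36 = 50.0% | 32.9 to 67.1 |

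Section 12.4.2 targets 75% and treats results substantially closer to 50% as not encouraging. At n = 36 that whole distance is 27 − 18 = 9 patients.

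**The case against.** The strongest reply is that recurrence in 10.1.6 is loose wording for any disease failure. The section sits under a PFS heading, does not cite Appendix C and does not use its term Relapse. Section 2.1 reports earlier cases as progressed/relapsed without separating the two, and 12.3.2 pairs a progression event with non-relapse mortality. This has weight: the authors may well have intended one class of disease failure. But 10.1.1 and 10.1.5, in the same chapter, point to the narrower reading, and an intended single class is a reason to write it down.

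A second reply is that progression without prior CR may be uncommon. Section 2.2 proposes transplant after some disease control, and 4.1.2 adds skin electron beam therapy for extensive skin disease. Disease status at transplant is not otherwise fixed, so the frequency is unknown. That stands, and it is why no size is claimed. It is also true that no sample-size figure or stopping rule uses EFS.

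A reader might go further in three ways that the documents do not support.
- That PFS counts only progression, or misses relapse after CR as a class. Section 12.3.2 requires patients to be alive, so death counts, and Appendix C PD includes loss of response from CR. Only the sub-threshold relapses of step 3 remain.
- That the earlier TLI/ATG study in section 2.2 sizes the bias: 18 − 10 = 8 of 18 + 17 = 35 patients with stated status were not reported to reach CR, which would scale to about 9 of 40. Not reaching CR is not progressing; a patient in lasting partial response is correctly event-free.
- That 10.1.6 is the only time-to-event definition before section 12. Section 10.1.5 defines duration of response.

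**Conclusion.** The point holds for EFS, and for the conflict over the primary endpoint. Followed as written, the EFS rule leaves out progression in patients who never reached CR until they die, and omitting failures can only raise the estimate. The size cannot be derived; the scale is 2.5 points per missed failure at n = 40. A patient whose progression is missed but who dies before the time point is already counted by then, so only patients still alive contribute.

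For PFS the finding is narrower. The primary endpoint has two competing event sets, one reached by the cross-reference in 12.1.1 and one in 12.3.2. The 12.3.2 version omits or delays only limited skin recurrence, low-level blood recurrence, or a new node not proven N3.

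The EFS conclusion assumes that recurrence in 10.1.6 has the sense it has in 10.1.1, 10.1.5 and Appendix C. If it was meant more broadly, the bias disappears, but the text still needs to say so, because the primary endpoint has no single stated definition.

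**What to change.** 1. In 10.1.6 and 12.3.2, define the event for both PFS and EFS once: the first of global PD (Appendix C), global Relapse (Appendix C) or death from any cause.
2. Correct the cross-reference in 12.1.1 so that it leads to that definition.
3. In 12.3.2, define the cumulative-incidence event as first PD or Relapse, with death without prior PD or Relapse as the competing event.
4. If EFS and PFS are then identical, keep one name throughout, including 1.1 and 12.1.2.

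The cost is wording only. Appendix C already supplies both categories, and the assessments in 4.1.6 and 10.1.1 already run to whichever comes first, so no new data are needed. The downside is that reported EFS, and possibly PFS, may be slightly less favourable.
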